## 9. Balance Assessment

Optum- <https://bwh-dope.aetion.com/projects/details/1069/results/63131/result/0>

MarketScan- <https://bwh-dope.aetion.com/projects/details/1072/results/63129/result/0>

Medicare- <https://bwh-dope.aetion.com/projects/details/1073/results/63128/result/0>

Date conducted: 12/22/2020

After review of initial feasibility and power analyses, complete creation of the remaining covariates from Section 6.2. Again, using the

dummy outcome of a 90-day gap in database enrollment, complete a 1:1 PS-matched analysis. The PS should include the complete list of covariates.

- Provide plot of PS distributions stratified by treatment group.

Note- Please refer to **Appendix B**.

- Report covariate balance after matching.

Note- For Table 1, please refer to **Appendix B**.

- Report reasons for censoring by treatment group.

	Overall	Referent	Exposure
Dummy outcome	0 (0%)	0 (0%)	0 (0%)
Death	150 (2.47%)	64 (2.11%)	86 (2.84%)
Start of an additional exposure	309 (5.09%)	106 (3.49%)	203 (6.69%)
End of Index Exposure	2285 (37.67%)	1206 (39.76%)	1079 (35.58%)
Specified date reached	1868 (30.79)	879 (28.98%)	989 (32.61%)
End of patient enrollment	696 (11.47%)	366 (12.07%)	330 (10.88%)
Switch to ARBs or Aliskiren + Nursing Home admission Occurred	758 (12.50%)	412 (13.58%)	346 (11.41%)

- Report follow-up time by treatment group.

Patient Group	Optum Median Follow-Up Time (Days) [IQR]	MarketScan Median Follow-Up Time (Days) [IQR]	Medicare Median Follow-Up Time (Days) [IQR]
Overall Patient Population	118 [58, 286]	139 [59, 296]	102 [46, 189]
Referent - ACE Inhibitors	126 [60, 309]	142 [77, 295]	102 [42, 170]
Exposure - Sacubitril/Valsartan	108 [56, 266]	136 [58, 300]	106 [58, 218]

- Report overall risk of the primary outcome.

	Optum	MarketScan	Medicare	Pooled
Risk per 1,000 patients	206.6	160.3	248.0	215.3

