# Appendix B: Sacubitril/Valsartan vs. ACE Inhibitors

Variable	OPTUM			MARKETSCAN			MEDICARE			POOLED		
	Reference - ACE Inhibitors	Exposure - Sacubitril/Valsartan	St. Diff	Reference - ACE Inhibitors	Exposure - Sacubitril/Valsartan	St. Diff	Reference - ACE Inhibitors	Exposure - Sacubitril/Valsartan Copy	St. Diff	Reference - ACE Inhibitors	Exposure - Sacubitril/Valsartan Copy	St. Diff
Number of patients	17,244	2,424		10,721	1,289		18,303	1,658		46,268	5,371	
Age - Continuous												
...mean (sd)	69.53 (11.82)	68.49 (12.18)	0.0867	63.95 (14.26)	60.92 (13.48)	0.2184	77.09 (8.22)	76.02 (7.61)	0.1351	71.23 (11.22)	69.00 (11.33)	0.1978
...median [IQR]	71.00 [63.00, 78.00]	70.00 [61.00, 78.00]	0.0833	63.00 [55.00, 75.00]	60.00 [52.00, 69.00]	0.2162	76.00 [70.00, 83.00]	75.00 [70.00, 81.00]	0.1262	71.12 (11.22)	69.14 (11.33)	0.1756
Age Categories												
...18 - 54; n (%)	1,882 (10.9%)	332 (13.7%)	-0.0853	2,583 (24.1%)	377 (29.2%)	-0.1155	0 (0.0%)	0 (0.0%)	#DIV/0!	4,465 (9.7%)	709 (13.2%)	-0.1101
...55 - 64; n (%)	3,133 (18.2%)	468 (19.3%)	-0.0282	3,626 (33.8%)	504 (39.1%)	-0.1103	0 (0.0%)	0 (0.0%)	#DIV/0!	6,759 (14.6%)	972 (18.1%)	-0.0947
...65 - 74; n (%)	5,925 (34.4%)	807 (33.3%)	0.0232	1,785 (16.6%)	169 (13.1%)	0.0985	7,965 (43.5%)	777 (46.9%)	-0.0684	13,890 (30.0%)	1,584 (29.5%)	0.0109
...>= 75; n (%)	6,304 (36.6%)	817 (33.7%)	0.0608	2,727 (25.4%)	239 (18.5%)	0.1673	10,338 (56.5%)	881 (53.1%)	0.0684	16,642 (36.0%)	1,698 (31.6%)	0.0931
Gender												
...Male; n (%)	11,865 (68.8%)	1,549 (63.9%)	0.1038	7,721 (72.0%)	882 (68.4%)	0.0788	10,308 (56.3%)	951 (57.4%)	-0.0222	22,173 (47.9%)	2,500 (46.5%)	0.0280
...Female; n (%)	5,379 (31.2%)	875 (36.1%)	-0.1038	3,000 (28.0%)	407 (31.6%)	-0.0788	7,995 (43.7%)	707 (42.6%)	0.0222	13,374 (28.9%)	1,582 (29.5%)	-0.0132
Region without zero category Copy												
...Northeast; n (%)	2,101 (12.2%)	273 (11.3%)	0.0280	2,048 (19.1%)	244 (18.9%)	0.0051	3,372 (18.4%)	321 (19.4%)	-0.0255	5,473 (11.8%)	594 (11.1%)	0.0220
...Midwest; n (%)	8,056 (46.7%)	1,390 (57.3%)	-0.2134	3,548 (33.1%)	302 (23.4%)	0.2167	7,376 (40.3%)	771 (46.5%)	-0.1253	15,432 (33.4%)	2,161 (40.2%)	-0.1414
...South; n (%)	3,985 (23.1%)	416 (17.2%)	0.1475	4,096 (38.2%)	636 (49.3%)	-0.2252	4,795 (26.2%)	357 (21.5%)	0.1105	8,780 (19.0%)	773 (14.4%)	0.1236
...West; n (%)	3,086 (17.9%)	342 (14.1%)	0.1038	1,015 (9.5%)	106 (8.2%)	0.0458	2,760 (15.1%)	209 (12.6%)	0.0724	5,846 (12.6%)	551 (10.3%)	0.0723

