# Appendix B: Sacubitril/Valsartan vs. ACE Inhibitors

Variable	AFTER MATCHING								POOLED				
	OPTUM			MARKETSCAN			MEDICARE		Reference - ACE Inhibitors		Exposure - Sacubitril/valsartan	St. Diff	
Reference - ACE Inhibitors	Exposure - Sacubitril/valsartan	St. Diff	Reference - ACE Inhibitors	Exposure - Sacubitril/valsartan	St. Diff	Reference - ACE Inhibitors	Exposure - Sacubitril/valsartan	St. Diff	Reference - ACE Inhibitors	Exposure - Sacubitril/valsartan	St. Diff		
Number of patients	1,279	1,279	748	748	0	1,006	1,006	0	3,033	3,033	0		
Age - Continuous	68.68 (11.85)	67.91 (12.31)	0.0637	59.59 (13.80)	60.00 (13.63)	-0.0299	75.41 (7.47)	75.61 (7.51)	-0.0267	68.67 (11.17)	68.51 (11.33)	0.0142	
...mean (sd)	69.00 [61.00, 77.00]	69.00 [60.00, 77.00]	0.0000	58.50 [51.00, 68.00]	60.00 [52.00, 68.00]	-0.1094	74.00 [69.00, 81.00]	75.00 [69.00, 81.00]	-0.1335	68.07 (11.17)	68.77 (11.33)	-0.0622	
Age Categories*	...18 - 54; n (%)	137 (10.7%)	196 (15.3%)	-0.1371	263 (35.2%)	236 (31.6%)	0.0764	0 (0.0%)	0 (0.0%)	#DIV/0!	400 (13.2%)	432 (14.2%)	-0.0291
...55 - 64; n (%)	285 (22.3%)	256 (20.0%)	0.0563	265 (35.4%)	284 (38.0%)	-0.0540	0 (0.0%)	0 (0.0%)	#DIV/0!	550 (18.1%)	540 (17.8%)	0.0078	
...65 - 74; n (%)	427 (33.4%)	411 (32.1%)	0.0277	111 (14.8%)	103 (13.8%)	0.0286	514 (51.1%)	492 (48.9%)	0.0440	941 (31.0%)	903 (29.8%)	0.0261	
...> 75; n (%)	430 (33.6%)	416 (32.5%)	0.0234	109 (14.6%)	125 (16.7%)	-0.0578	492 (48.9%)	514 (51.1%)	-0.0440				
Gender	...Male; n (%)	880 (68.8%)	855 (66.8%)	0.0428	541 (72.3%)	535 (71.5%)	0.0178	589 (58.5%)	604 (60.0%)	-0.0305	1,469 (48.4%)	1,459 (48.1%)	0.0060
...Female; n (%)	399 (31.2%)	424 (33.2%)	-0.0428	207 (27.7%)	213 (28.5%)	-0.0178	417 (41.5%)	402 (40.0%)	0.0305	816 (26.9%)	826 (27.2%)	-0.0068	
Region without zero category	...Northeast; n (%)	142 (11.1%)	140 (10.9%)	0.0064	137 (18.3%)	142 (19.0%)	-0.0180	159 (15.8%)	195 (19.4%)	-0.0946	301 (9.9%)	335 (11.0%)	-0.0360
...Midwest; n (%)	722 (56.5%)	715 (55.9%)	0.0121	202 (27.0%)	180 (24.1%)	0.0665	482 (47.9%)	469 (46.6%)	0.0260	1,204 (39.7%)	1,184 (39.0%)	0.0143	
...South; n (%)	227 (17.7%)	247 (19.3%)	-0.0412	370 (49.5%)	366 (48.9%)	0.0120	232 (23.1%)	221 (22.0%)	0.0263	459 (15.1%)	468 (15.4%)	-0.0083	
...West; n (%)	188 (14.7%)	177 (13.8%)	0.0257	39 (5.2%)	60 (8.0%)	-0.1130	133 (13.2%)	121 (12.0%)	0.0362	321 (10.6%)	298 (9.8%)	0.0264	
...Unknown+missing; n (%)	0 (0.0%)	0 (0.0%)	#DIV/0!	0 (0.0%)	0 (0.0%)	#DIV/0!							

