...median (IQR)	15.93 [5.74, 32.88]	18.14 [6.52, 33.73]	-0.0600	10.53 [3.58, 20.38]	12.40 [5.11, 19.94]	-0.1150	16.10 [5.26, 32.03]	18.78 [5.57, 34.95]	-0.0796	14.65 (36.11)	16.94 (26.88)	-0.0719
SES Proxy - Low income indicator; n (%)	275 (21.5%)	299 (23.4%)	-0.0455	0 (0.0%)	0 (0.0%)	#DIV/0!	0 (0.0%)	0 (0.0%)	#DIV/0!	275 (9.1%)	299 (9.9%)	-0.0273
SES Proxy - Business type												
...Commercial; n (%)	325 (25.4%)	340 (26.6%)	-0.0274	0 (0.0%)	0 (0.0%)	#DIV/0!	0 (0.0%)	0 (0.0%)	#DIV/0!	325 (10.7%)	340 (11.2%)	-0.0160
...Medicare; n (%)	954 (74.6%)	939 (73.4%)	0.0274	0 (0.0%)	0 (0.0%)	#DIV/0!	0 (0.0%)	0 (0.0%)	#DIV/0!	954 (31.5%)	939 (31.0%)	0.0108
SES Proxy - Insurance Plan type												
...Comprehensive; n (%)	0 (0.0%)	0 (0.0%)	#DIV/0!	105 (14.0%)	94 (12.6%)	0.0412	0 (0.0%)	0 (0.0%)	#DIV/0!	105 (3.5%)	094 (3.1%)	0.0224
...HMO; n (%)	0 (0.0%)	0 (0.0%)	#DIV/0!	62 (8.3%)	71 (9.5%)	-0.0422	0 (0.0%)	0 (0.0%)	#DIV/0!	062 (2.0%)	071 (2.3%)	-0.0207
...PPD; n (%)	0 (0.0%)	0 (0.0%)	#DIV/0!	403 (53.9%)	400 (53.5%)	0.0080	0 (0.0%)	0 (0.0%)	#DIV/0!	403 (13.3%)	400 (13.2%)	0.0029
...Others; n (%)	0 (0.0%)	0 (0.0%)	#DIV/0!	178 (23.8%)	183 (24.5%)	-0.0164	0 (0.0%)	0 (0.0%)	#DIV/0!	178 (5.9%)	183 (6.0%)	-0.0042
SES Proxy - Dual status code (with Medicaid); n (%)	0 (0.0%)	0 (0.0%)	#DIV/0!	0 (0.0%)	0 (0.0%)	#DIV/0!	202 (20.1%)	203 (20.2%)	-0.0025	202 (6.7%)	203 (6.7%)	0.0000

\*Excluded from P5 model: Age Categories, Use of Lithium, Use of AGI & Meglitinides, PCSK9 Inhibitors, Use of heparin or LMWH, Hemodialysis/Peritoneal dialysis

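### In Optum, PS matching with the age categories left out of the model did not remove the under-55 imbalance (10.7% vs 15.3%, standardized difference -0.137), although mean and median age look balanced

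*Protocol*

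**What the plan says.** Protocol Section 9 (Balance Assessment) asks for a 1:1 PS match on a dummy outcome and states "The PS should include the complete list of covariates". Section 6.2 refers to Table 1 in Appendix B for that list, and the table has both a continuous age row and an Age Categories block.

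In the after-matching table the Age Categories block carries an asterisk. Its footnote reads "Excluded from P5 model: Age Categories, Use of Lithium, Use of AGI & Meglitinides", followed by PCSK9 inhibitors, heparin or LMWH and dialysis. Continuous age is not among the excluded items, so it appears to carry age in the model alone.

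For the 18-54 band in Optum (ACE inhibitors, then sacubitril/valsartan, then standardized difference), Appendix B gives:

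- before matching: "1,882 (10.9%) 332 (13.7%) -0.0853"
- after matching: "137 (10.7%) 196 (15.3%) -0.1371"

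The section that follows Section 9 (Final Power Assessment) stops the analyses until balance and power have been reviewed. The protocol states no numerical limit for acceptable balance.

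**The concern.** Age is a basic prognostic factor. A PS with age as a single continuous term can balance the mean and leave a tail of the distribution unbalanced, and the Optum table shows that pattern. More patients under 55 are in the sacubitril/valsartan arm. If they have the lower outcome rate, the Optum HR moves toward benefit, the same direction as the RCT result being replicated (HR 0.80).

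Matching and power are reported separately for each database, so balance within a database matters. The pooled column does not show this gap.

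**Working it through.** **Inputs.** All counts are from Appendix B, before and after matching. Expected events are from the Final Power Assessment tables.

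**1. Reproduce the printed figures.** For proportions, d = (p_ref - p_exp) / sqrt{[p_ref(1-p_ref) + p_exp(1-p_exp)]/2}.

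| Optum, age 18-54 | ACE inhibitors | Sacubitril/valsartan | d from printed % | d from counts |
|---|---|---|---|---|
| Before matching | 1,882/17,244 | 332/2,424 | -0.0853 | -0.0848 |
| After matching | 137/1,279 | 196/1,279 | -0.1371 | -0.1374 |

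The rounded percentages reproduce both printed values. The matched bands sum to 1,279 in each arm (137+285+427+430 and 196+256+411+416), so the row is not a misprint.

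**2. Size of the matched gap.** It is 196 - 137 = 59 patients, or 4.6 percentage points. An unpaired two-proportion test gives z = 3.47, p = 0.0005. This is only a guide, because the data are matched and the cell was picked from a long table. The other Optum bands are at 0.056, 0.027 and 0.023 (from counts). Mean age is 68.68 vs 67.91 (0.0637), and both medians are 69.00.

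**3. Why the figure before matching is lower.** Before matching, 1,288 of 2,424 exposed Optum patients had ACE-inhibitor use. After matching, 1,279 of 1,279 did. If that row means the same in both tables, the matched exposed patients come from those 1,288, and only 9 of the 1,288 were not matched. The number under 55 among the 1,288 therefore lies between 196 and 196 + 9 = 205.

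- 196/1,288 = 15.2%, against 1,882/17,244 = 10.9%: d = -0.128
- 205/1,288 = 15.9%, against 10.9%: d = -0.147

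The gap among matchable patients was thus already about -0.13 to -0.15. The ACE-inhibitor share hardly moved (10.9% to 10.7%), while the exposed share rose from 13.7% to 15.3% as patients without ACE-inhibitor use dropped out.

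**4. The other databases.**

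- MarketScan: 263/748 (35.2%) vs 236/748 (31.6%), printed d = 0.0764, z = 1.48, p = 0.14. Before matching it was -0.1155.
- Medicare: no patients under 55.
- Pooled: 137+263 = 400 vs 196+236 = 432 of 3,033, printed d = -0.0291. The opposite MarketScan sign offsets part of the Optum gap.

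**5. Possible bias.** Let r be the under-55 outcome rate divided by the rate at 55 or older. The documents do not give r; 0.5 to 0.7 is an assumption. With no treatment effect and no other imbalance, the apparent rate ratio is [1 - p_exp(1-r)] / [1 - p_ref(1-r)].

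| | r = 0.5 | r = 0.7 |
|---|---|---|
| Optum (p_exp 0.153, p_ref 0.107) | 0.976 | 0.986 |
| Pooled (p_exp 0.142, p_ref 0.132) | 0.994 | 0.997 |

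Optum: 1.4% to 2.4% toward benefit. Pooled: 0.3% to 0.6%. For scale, with 528 expected Optum events the standard error of log HR is about 2/sqrt(528) = 0.087, so the worst case, |ln 0.976| = 0.024, is about 0.28 standard errors.

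**The case against.** A reader might infer that dropping the age categories made matching worsen the imbalance, from -0.085 to -0.137. The documents do not support this. The two figures describe different exposed populations, and among the patients who could be matched the gap was already about -0.13 to -0.15 (step 3). The accurate statement is that matching did not remove the gap.

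Nor is the cause proven. MarketScan had the same exclusion, yet its absolute under-55 difference fell from 0.116 to 0.076. A reader might also infer a biased MarketScan HR and artificial heterogeneity between databases; a difference below 0.1 with p of about 0.14 is too weak for that.

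It is also fair to say that age is adjusted: continuous age is not listed as excluded, and its matched differences are 0.064, -0.030 and -0.027 in Optum, MarketScan and Medicare. Leaving out categories that duplicate a continuous term is an ordinary and openly footnoted choice. Under 65 in Optum, the gap is only 422 vs 452 of 1,279 (-0.049), so 55 is the cut-point where it looks largest. The pooled analysis, with stated power 0.98, is hardly affected.

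These arguments limit the size and the causal claim. They do not remove a difference above 0.1 in a prognostic factor, in the largest matched database, at a review step meant to find such differences.

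**Conclusion.** The point holds in a limited form and is minor. PS matching in Optum left an under-55 imbalance of -0.137 that the mean and median do not show and the pooled figure largely hides. Whether omission of the age categories produced it cannot be settled from the documents, although a single continuous term is a plausible reason why it remained. The likely bias is 1.4% to 2.4% toward benefit on the Optum HR and below 1% on the pooled HR. Both figures rest on the assumed rate ratio of 0.5 to 0.7 and on the under-55 share being the only difference between the arms. The 0.1 benchmark is a convention, not a protocol rule.

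**What to change.** At the Section 9 review step, before outcomes are run, add the four age categories already defined (or a spline of age) to the Optum PS beside continuous age, and do the same in MarketScan and Medicare for consistency. Re-match, and report the age-band differences within each database against 0.1, stating that this is a conventional limit. Reword Section 9 or the footnote so that they agree on what the PS contains.

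The cost is one PS refit and re-match per database, with no outcome data seen. The number of matched pairs may change a little. By how much cannot be worked out without patient data, so the new numbers should go into the final power table.
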